Rationale for the study and study design	
• Rationale for the study 
Using advanced technology in 2010, researchers from the University of California, San Francisco identified Deoxyribonucleic acid (DNA) fragments of Porcine circovirus type 1 (PCV-1) in Rotarix. Further investigations conducted by GSK and the United States (US) Food and Drug Administration (FDA) confirmed the presence of PCV-1 DNA fragments in Rotarix and its starting materials. Low levels of PCV-1 viral particles were also detected during the production process and in the final container. Retrospective laboratory investigations conducted by GSK on 40 human rotavirus (HRV) vaccine recipients showed that none of the subjects who received the HRV vaccine demonstrated seroconversion to PCV-1, however, PCV-1 from the vaccine was identified in the stool samples of 4 infants from the HRV group (at Day 3 and Day 7 post Dose 1). The detection of PCV-1 DNA only at the earliest time-points post-vaccination was consistent with transient passage of DNA through the infants' digestive tracts without replication. Lack of PCV-1 infection is further supported by the absence of anti-PCV-1 antibody in the HRV vaccine recipients, including the infants who had PCV-1 DNA detected in their stool samples [Dubin, 2013]. In a follow-up retrospective laboratory analysis of samples of 596 subjects, a post-vaccination anti-PCV-1 antibody seropositivity rate of 1% [90% Confidence Interval (CI): 0.3-2.6] in recipients of the human RV vaccine (3/299 samples) and 0.3% [90% CI: 0.0-1.6] in the placebo group (1/296 samples) was observed. The difference in the post-vaccination seropositivity and the seroconversion rates between the two study groups were -0.66 [90% CI: -2.16-0.60] and -0.33 [90% CI: -1.70-0.89], respectively. The 90% CI for both group differences included 0, indicating that there was no statistically significant increase as compared to the placebo

[Han, 2016]. Therefore, currently available data does not suggest occurrence of PCV-1 infection in infants who received *Rotarix* in clinical trials. These results are consistent with published literature which indicates that PCV-1 is not capable of causing infection in humans [Hattermann, 2004a; Hattermann, 2004b].

GSK has replaced the cell bank and virus seeds used as base production material for its HRV vaccine. In accordance with the regulators, the company continues to manufacture *Rotarix* to the existing standards of approved production and quality, to meet public health needs worldwide.

This study will assess if there is any immune interference between the PCV-free liquid HRV vaccine and routine infant vaccinations currently in use in the US, namely *Pediarix*, *Hiberix* and *Prevenar 13* as compared to the currently licensed lyophilized formulation of the HRV vaccine when co-administered with the same routine vaccinations.

- Rationale for the study design

The study is designed as a randomized, controlled, single-blind study with two parallel groups. This study will evaluate the immunogenicity, reactogenicity and safety of the vaccines *Pediarix*, *Hiberix* and *Prevenar 13* that are recommended for children in the US during the first year of life, when co-administered with the PCV-free liquid HRV vaccine as compared to the licensed lyophilized vaccine.

The currently licensed lyophilized *Rotarix* vaccine co-administered with routine infant vaccines in the US has been shown not to impair the immune response to any of the co-administered antigens [Dennehy 2008]. Therefore, the use of the currently licensed lyophilized vaccine as the control is considered appropriate. Furthermore, this study design will avoid logistical constraints related to the inclusion of co-administration and separate administration of US routine infant vaccines in the same study.

An Independent Data Monitoring Committee (IDMC), consisting of clinical experts and a biostatistician will review the safety data periodically to monitor the safety aspects of the PCV-free liquid HRV vaccine.

This study will have a single-blind design to ensure that the subject's parent(s)/Legally Acceptable Representative(s) (LARs) are not influenced by the knowledge of the *Rotarix* formulation when reporting safety events and when

complying with the study procedure.

Objectives

Co-Primary

- To demonstrate the non-inferiority of the immune responses to three doses of Pediarix, Hiberix and Prevenar 13 when co-administered with two doses of the PCV-free liquid HRV vaccine, as compared to when co-administered with the currently licensed lyophilized HRV vaccine, 1 month after Dose 3 of routine infant vaccines.

Criteria for non-inferiority:

- *Lower limits of the two-sided standardized asymptotic 95% confidence intervals (CIs) on the differences between groups (HRV Liq group minus HRV Lyo group) in the percentages of subjects with seroprotective concentrations (≥ 0.1 IU/mL) for each of anti-diphtheria (anti-D) and anti-tetanus (anti-T) antibodies are $\geq 10\%$ (clinical limit for non-inferiority),*
- *The lower limit of the two-sided standardized asymptotic 95% CI on the difference between groups (HRV Liq group minus HRV Lyo group) in the percentages of subjects with seroprotective concentration (≥ 10 mIU/mL) for antibodies against hepatitis B surface antigen (anti-HBs) is $\geq 10\%$ (clinical limit for non-inferiority),*
- *Lower limits of the two-sided standardized asymptotic 95% CIs on the differences between groups (HRV Liq group minus HRV Lyo group) in the percentages of subjects with seroprotective titers (≥ 8 ED₅₀) for each of anti-poliovirus serotypes 1, 2 and 3 antibodies are $\geq 5\%$ (clinical limit for non-inferiority),*
- *Lower limits of the two-sided 95% CIs on the geometric mean antibody concentrations (GMC) ratios (HRV Liq group over HRV Lyo group) for antibodies against each of the pertussis toxoid (PT), filamentous hemagglutinin (FHA) and pertactin (PRN) antigens [anti-PT, anti-FHA and anti-PRN] are ≥ 0.67 (clinical limit for non-inferiority),*
- *Lower limits of the two-sided 95% CIs on the GMC ratios (HRV Liq group over HRV Lyo group) for each of the 13 Streptococcus pneumoniae (S. pneumoniae) serotypes are ≥ 0.5 (clinical limit for*

non-inferiority),

Secondary

Immunogenicity:

- To assess the immunogenicity of the PCV-free liquid HRV vaccine and currently licensed lyophilized HRV vaccine in terms of serum anti-rotavirus immunoglobulin A (IgA) antibody seropositivity rate at Visit 4, 3 months after Dose 2 of the HRV vaccine.
- To assess the immunogenicity of routine infant vaccines *Pediarix*, *Hiberix* and *Prevenar 13* when co-administered with the PCV-free liquid HRV vaccine and currently licensed lyophilized HRV vaccine at Visit 4, 1 month after Dose 3 of routine infant vaccines.

Reactogenicity and safety:

- To assess the reactogenicity of the PCV-free liquid HRV vaccine and currently licensed lyophilized HRV vaccine in terms of general solicited adverse events (AEs) during the 8 day (Day 1-Day 8) follow-up period after each dose of HRV vaccine.
- To assess the safety of the study vaccines in terms of unsolicited AEs during the 31 day (Day 1-Day 31) follow-up period after each dose of HRV vaccine and serious adverse events (SAEs) during the entire study period.
- Study design
 - Experimental design: Phase IIIA, single-blind, randomized, controlled, multi-centric study with two parallel groups.
 - Duration of the study: The total duration of the study, per subject, will be approximately 10 months including the 6 months of Extended Safety Follow-Up (ESFU) period after the last dose of study vaccine administered.
 - Epoch 001: Primary starting at Visit 1 (Day 1) and ending at the ESFU contact (Month 10).
 - Primary completion Date (PCD): Last subject attending Visit 4.
 - End of Study (EoS): Last testing results released for samples collected at Visit 4. If the last testing results are available before the Last Subject Last Visit (LSLV), i.e., before the ESFU, the EoS will then be the LSLV.
 - Study groups:

The study groups and the epoch foreseen in the study are provided in Synopsis Table 1.

The study groups and the treatment foreseen in the study are provided in Synopsis Table 2.

Synopsis Table 1 Study groups and epoch foreseen in the study

Study groups	Number of subjects	Age at Dose 1 (Min/Max)	Epoch 001
HRV Liq	640	6 weeks-12 weeks	•
HRV Lyo	640	6 weeks-12 weeks	•

Synopsis Table 2 Study groups and treatment foreseen in the study

Treatment name	Vaccine name	Study Groups	
		HRV Liq	HRV Lyo
HRV Liquid	HRV PCV-free	x	
HRV Lyophilized	HRV*		x
Pediarix	DTPa-HBV-IPV	x	x
Hiberix	Hib	x	x
Prevenar 13	Prevenar 13	x	x

*Licensed lyophilized HRV vaccine.

- Control: active control-GSK Biologicals' currently licensed lyophilized HRV vaccine.
- Vaccination schedule: Two doses of HRV vaccine to be administered according to a 0, 2 month schedule as per the immunization schedule for HRV vaccine administration in the US.

Co-administration of routine childhood vaccines *Pediarix*, *Hiberix* and *Prevenar 13* will be performed as follows:

- All the subjects will receive a dose each of *Pediarix*, *Hiberix* and *Prevenar 13* at Visit 1 (Day 1), Visit 2 (Month 2) and Visit 3 (Month 4).
- The routine booster dose for the co-administered vaccines will not be administered to subjects as a part of this study. Subject's parent(s)/LARs will be reminded at Visit 4 to consult their primary health care provider regarding the booster dose of the vaccines for their child.

- Treatment allocation: Randomized 1:1 using GSK Biologicals' Randomization System on Internet (SBIR).
- Blinding: single-blind.

The blinding of the study epoch is provided in Synopsis Table 3.

Synopsis Table 1 Blinding of study epoch

Study Epoch	Blinding
Epoch 001	single-blind

- Sampling schedule: Details of the samples to be collected are as follows:
 - Blood samples will be collected from all subjects at Visit 4 (Month 5) to measure serum anti-RV IgA antibody concentrations and antibody concentrations/titers against all the antigens in the co-administered vaccines.
- Type of study: self-contained.
- Data collection: Electronic Case Report Form (eCRF).
- Safety monitoring: An IDMC consisting of clinical experts and a biostatistician will review the safety data by treatment group periodically to monitor the safety aspects of the PCV-free liquid HRV vaccine.

Number of subjects The target will be to enrol 1280 eligible subjects who will be randomly assigned to two study groups in a (1:1) ratio (approximately 640 subjects in each group).

Endpoints**Primary**

- Immunogenicity with respect to components of the routine infant vaccines, one month after Dose 3 of routine infant vaccines (Visit 4):
 - Anti-D antibody concentration ≥ 0.1 IU/mL,
 - Anti-T antibody concentration ≥ 0.1 IU/mL,
 - Anti-HBs antibody concentrations ≥ 10 mIU/mL,
 - Anti-poliovirus types 1, 2 and 3 antibody titers ≥ 8 ED₅₀,
 - Anti-PT, anti-FHA and anti-PRN antibody concentrations expressed as GMCs,
 - Anti-pneumococcal serotypes (1, 3, 4, 5, 6A, 6B, 7F, 9V, 14, 18C, 19A, 19F, 23F) antibody concentrations expressed as GMCs,
 - Anti-PRP antibody concentrations ≥ 0.15 μ g/mL,
 - Anti-PRP antibody concentrations ≥ 1.0 μ g/mL.
- Difference in seroresponse with respect to PT, FHA and PRN antigen components one month after Dose 3 of routine infant vaccines (Visit 4):
 - Seroresponse to anti-PT, anti-FHA and anti-PRN.

Secondary

- Serum anti-rotavirus IgA antibody seropositivity 3 months after Dose 2 of HRV vaccine (Visit 4).
 - Serum anti-RV IgA antibody concentrations ≥ 20 U/mL and ≥ 90 U/mL 1-2 months after Dose 2.
- Immunogenicity with respect to components of the routine infant vaccines, one month after Dose 3 of routine infant vaccines (Visit 4):
 - PT, anti-FHA and anti-PRN antibody concentrations ≥ 2.693 IU/mL, ≥ 2.046 IU/mL and ≥ 2.187 IU/mL, respectively.
 - Anti-pneumococcal serotypes (1, 3, 4, 5, 6A, 6B, 7F, 9V, 14, 18C, 19A, 19F, 23F) antibody concentrations ≥ 0.35 μ g/mL for the ELISA,
 - Anti-D, anti-T, anti-PRP and anti-HBs antibody concentrations expressed as GMCs and anti-poliovirus types 1, 2 and 3 antibody concentrations expressed as Geometric Mean Titers (GMTs).
- Occurrence of general solicited AEs during the 8 day (Day 1-Day 8) follow-up period after each dose of HRV vaccine.
- Occurrence of unsolicited AEs within 31 days (Day 1-Day 31) after any dose of HRV vaccine, according to the Medical Dictionary for Regulatory Activities (MedDRA) classification.
- Occurrence of SAEs from Dose 1 of study vaccines up to study end.

TABLE OF CONTENTS

	PAGE
SPONSOR INFORMATION	6
SYNOPSIS.....	7
LIST OF ABBREVIATIONS	21
GLOSSARY OF TERMS	25
TRADEMARKS	29
1. INTRODUCTION.....	30
1.1. Background	30
1.2. Rationale for the study and study design	31
1.2.1. Rationale for the study	31
1.2.2. Rationale for the study design.....	32
1.3. Benefit: Risk Assessment	32
1.3.1. Risk Assessment	33
1.3.2. Benefit Assessment	35
1.3.3. Overall Benefit: Risk Conclusion	35
2. OBJECTIVES.....	35
2.1. Co-Primary objectives.....	35
2.2. Secondary objectives.....	36
3. STUDY DESIGN OVERVIEW	37
4. STUDY COHORT.....	39
4.1. Number of subjects/centers	39
4.2. Inclusion criteria for enrollment	39
4.3. Exclusion criteria for enrollment.....	40
5. CONDUCT OF THE STUDY	41
5.1. Regulatory and ethical considerations, including the informed consent process.....	41
5.2. Subject identification and randomization	43
5.2.1. Subject identification.....	43
5.2.2. Randomization of treatment.....	43
5.2.2.1. Randomization of supplies.....	43
5.2.2.2. Treatment allocation to the subject	43
5.2.2.2.1. Study group and treatment number allocation	43
5.2.2.2.2. Treatment number allocation for subsequent doses	44
5.3. Method of blinding	44
5.4. General study aspects	44
5.5. Outline of study procedures	44
5.6. Detailed description of study procedures	46
5.6.1. Informed consent	46

5.6.2.	Check inclusion and exclusion criteria	47
5.6.3.	Collect demographic data	47
5.6.4.	Medical and vaccination history	47
5.6.5.	Physical examination	47
5.6.6.	Check contraindications, warnings and precautions to vaccination.....	47
5.6.7.	Assess pre-vaccination body temperature	47
5.6.8.	Study group and treatment number allocation.....	48
5.6.9.	Sampling.....	48
5.6.9.1.	Blood sampling for immune response assessments	48
5.6.10.	Study Vaccines administration.....	48

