10.3. Determination of sample size

The target sample size is 832 subjects evaluable for immunogenicity analyses at Visit 4 (416 subjects in each group). Assuming that approximately 35% of enrolled subjects might withdraw or not be evaluable for analyses of immunogenicity, the target sample size to be enrolled is 1280 subjects (640 subjects in each group).

The primary objective of this study is to demonstrate the immune response elicited to all antigens contained in each of the routine infant vaccines *Pediarix*, *Hiberix* and *Prevenar 13* when co-administered with PCV-free liquid HRV vaccine is non-inferior to that elicited when co-administered with the lyophilized HRV vaccine.

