10.5. Derived and transformed data

- A seronegative subject is a subject whose antibody concentration is below the cut-off value.
- A seropositive subject is a subject whose antibody concentration is greater than or equal to the cut-off value. The applicable thresholds are presented in [Table 7](#).
- A seroprotected subject is a subject whose antibody concentration is greater than or equal to the level defining clinical protection. The following seroprotection thresholds are applicable:
 - anti-D antibody concentrations ≥ 0.1 IU/mL.
 - anti-T antibody concentrations ≥ 0.1 IU/mL.
 - anti-HBs antibody concentrations ≥ 10 mIU/mL.
 - anti-poliovirus types 1, 2 and 3 antibody titers ≥ 8 ED50.
 - anti-PRP antibody concentrations ≥ 0.15 μ g/mL.
- Other cut-offs to be considered:
 - anti RV IgA antibody concentration ≥ 90 U/mL.
 - anti-pneumococcal serotypes (1, 3, 4, 5, 6A, 6B, 7F, 9V, 14, 18C, 19A, 19F, 23F) antibody concentrations ≥ 0.35 μ g/mL for the ELISA.
 - anti-PRP antibody concentrations ≥ 1.0 μ g/mL.
- The GMC calculation will be performed by taking the anti-log of the mean of the log concentration transformations. Note that antibody concentrations below the cut-off of the assay will be given an arbitrary value of half the cut-off while antibody concentration above the assay cut-off but below the Limit of Quantification will be given the assay cut-off as value.

Handling of missing data:

Immunogenicity:

- For a given subject and a given immunogenicity measurement, missing or non-evaluable measurements will not be replaced.

Reactogenicity and Safety:

- For analysis of solicited, unsolicited AEs (such as SAEs or AEs by primary MedDRA term), and for the analysis of concomitant medications, all vaccinated subjects will be considered. Subjects who did not report the event or the concomitant medication will be considered as subjects without the event or the concomitant medication respectively.

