10.8. Analysis of safety

The ES will be used for the analysis of safety.

The following calculations will be performed for each group:

The percentage of doses and of subjects reporting at least one symptom (solicited or unsolicited) during the 8 day (Day 1-Day 8) solicited follow-up period post-vaccination will be computed, along with exact 95% CI. The same calculations will be done for symptoms (solicited or unsolicited) rated as grade 3 in intensity, those assessed as causally related to vaccination, those rated as grade 3 in intensity with causal relationship to vaccination and those that resulted in a medically attended visit.

The percentage of doses and of subjects reporting each individual solicited general symptom will be computed, over the 8 day (Day 1-Day 8) solicited follow-up period post-vaccination, along with exact 95% CI. The same calculations will be done for each individual general solicited symptom rated as grade 3 in intensity, those assessed as causally related to vaccination, those rated as grade 3 in intensity with causal relationship to vaccination and those that resulted in a medically attended visit. For fever, additional analyses will be performed by 0.5°C increments. These calculations will also be performed by sex and race.

The verbatim reports of unsolicited AEs will be reviewed by a physician and the signs and symptoms will be coded according to MedDRA. Every verbatim term will be matched with the appropriate Preferred Term. The percentage of subjects with unsolicited AEs occurring within 31 day (Day 1-Day 31) follow-up period after any dose with its exact 95% CI will be tabulated by group, and by preferred term. Similar tabulation will be done for unsolicited AEs rated as grade 3, for unsolicited AEs with causal relationship to vaccination, for unsolicited AEs rated as grade 3 with causal relationship to vaccination and those that resulted in a medically attended visit.

The percentage of subjects who started taking at least one concomitant medication, antipyretic medication and prophylactic antipyretic medication during the 8 day (Days 1-8) and 31 day (Days 1-31) follow-up period post-vaccination will be tabulated by dose, overall per subject and over all the doses.

Subjects who experienced at least one SAE during the entire study period (from Dose 1 till ESFU Contact at Month 10) will be reported and the SAEs will be described in detail.

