5.3. Important protocol deviation not leading to elimination from per-protocol analysis set

Important protocol deviations not leading to elimination from PPS for immunogenicity will be reported by groups. This includes but is not limited to

- Forced randomization: In case of supplies shortage for the next assigned vaccine according to the randomization schedule at the clinical site, the randomization system will use the forced randomization procedure in order to continue to enrol and vaccinate subjects. The system moves seamlessly to the next treatment/randomization number for which vaccine supplies are available. The site will not be aware of the forced randomization event.
- Manual randomization: In case the randomization system is unavailable, the investigator has the option to perform randomization by selecting supplies available at the site according to a pre-defined rule.
- Short follow-up: subjects who completed the last study contact before the minimum length of follow-up requirement (180 days).
- HRV vaccination without documentation of solicited symptoms i.e. for a HRV vaccine dose administered, at least one solicited symptom is not documented as being present or absent.

The full list of reportable protocol deviations is available in the study protocol deviation management plan.

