11.2.5. Safety

In case there will be more than 5% of subjects without documented dose for solicited symptoms (i.e., symptom screen not completed), sensitivity analysis will include only vaccinated subjects for doses with documented safety data (i.e., symptom screen completed).

For analysis of solicited, unsolicited adverse events (such as serious adverse events or adverse events by primary MedDRA term) and for the analysis of concomitant medications, all vaccinated subjects will be considered. Subjects who did not report the event or the concomitant medication will be considered as subjects without the event or the concomitant medication respectively.

The following rules will be used for the analysis of solicited symptoms:

- Subject who didn't document the presence or absence of a solicited symptom after one dose will be considered not having that symptom after that dose in the analysis done on "administered dose"
- Subjects who documented the absence of a solicited symptom after one dose will be considered not having that symptom after that dose.
- Subjects who documented the presence of a solicited symptom and fully or partially recorded daily measurement over the solicited period will be included in the summaries at that dose and classified according to their maximum observed daily recording over the solicited period.
- Subjects who documented the presence of a solicited symptom after one dose without having recorded any daily measurement will be considered as having that symptom after that dose (at the lowest intensity).
- Intensity of the following solicited AEs will be assessed as described in [Table 8](#) and [Table 9](#).

Table 8 Intensity scales to be used by the parent(s)/LAR(s) for solicited symptoms during the solicited follow-up period

Adverse Event	Intensity grade	Parameter
Fever*		Record temperature in °C/°F using any age-appropriate route.
Irritability/Fussiness	0	Behavior as usual
	1	Crying more than usual/no effect on normal activity
	2	Crying more than usual/interferes with normal activity
	3	Crying that cannot be comforted/prevents normal activity
Diarrhea\$		Record the number of looser than normal stools/day
Vomiting§		Record the number of vomiting episodes/day
Loss of appetite	0	Appetite as usual
	1	Eating less than usual/no effect on normal activity
	2	Eating less than usual/interferes with normal activity
	3	Not eating at all
Cough/runny nose	0	Normal
	1	Cough/runny nose which is easily tolerated

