Solicited general symptom	Primary analysis: all subjects with study vaccine administered Sensitivity analysis: all subjects with at least one solicited general symptom documented as either present or absent (i.e., symptom screen completed)	Primary analysis: all study visits with study vaccine administered Sensitivity analysis: all study visits with study vaccine administered and with at least one solicited general symptom documented as either present or absent (i.e., symptom screen completed)
Unsolicited symptom	All subjects with study vaccine administered	All study visits with study vaccine administered
Concomitant medication	All subjects with study vaccine administered	All study visits with study vaccine administered

For summaries by MedDRA primary preferred term combining solicited and unsolicited adverse events, solicited adverse events will be coded as per the following MedDRA codes

Solicited symptom	Lower level term code	Corresponding Lower level term decode
Fever	10016558	Fever
Irritability/Fussiness	10022998	Irritability
Diarrhoea	10012727	Diarrhoea
Vomiting	10047700	Vomiting
Loss of appetite	10003028	Appetite lost
Cough/runny nose	10011224	Cough

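### The rule that no report means no event also covers time after last contact, so the Month 10 SAE percentage in each group is somewhat understated

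*Protocol*

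**What the plan says.** The secondary endpoint is "Occurrence of SAEs from Dose 1 of study vaccines up to study end" (Protocol synopsis and 10.2; SAP 4.2). On duration the protocol states: "The total duration of the study, per subject, will be approximately 10 months including the 6 months of Extended Safety Follow-Up (ESFU) period". The text specific to SAEs, in Protocol 10.8 and SAP 6.4.1, says: "Subjects who experienced at least one SAE during the entire study period (from Dose 1 till ESFU Contact at Month 10) will be reported". It names no estimator, confidence interval or person-time.

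The counting rule is in Protocol 10.5: "Subjects who did not report the event or the concomitant medication will be considered as subjects without the event or the concomitant medication respectively". SAP 11.2.5 repeats it, and its scope includes SAEs by name: "For analysis of solicited, unsolicited adverse events (such as serious adverse events or adverse events by primary MedDRA term". The denominator table in SAP 11.2.5 has no row for SAEs. Its row for unsolicited symptoms uses "all subjects with study vaccine administered". In the SAP's list of templates, Template 23 is a number and percentage of subjects with SAEs on the Exposed Set. The titles of Templates 23 and 24 stop at Visit 3, which in this study is Month 4.

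Protocol 9.2.1 defines a withdrawal as a subject about whom nothing further is collected after the last contact, and says data up to that point are used. The only safety sensitivity analysis (SAP 6.4.2 and 11.2.5) concerns solicited symptoms on documented doses.

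**The concern.** A percentage labelled as the risk of an SAE from Dose 1 to Month 10 should reflect what was observed over that window. Under the stated rule, an infant last seen at Month 2 contributes a full 10 months of apparent freedom from SAEs, of which 8 were unobserved. The rule thus turns absence of observation into absence of an event, although Protocol 9.2.1 recognises that nothing is known after last contact.

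The visit schedule makes such gaps plausible. After Visit 4 at Month 5, the only scheduled SAE contact is the single safety call at Month 10. An infant who attends every visit but is not reached for that call has about half the window unobserved and is still counted as SAE-free throughout.

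SAEs over the entire study are a stated safety objective for the new formulation, so the figure will be read as a 10-month risk.

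**Working it through.** **The plan's own figures.** The documents state no SAE rate and no power for SAEs. Their one attrition figure reproduces: 832 / (1 − 0.35) = 1280, or 416 / 0.65 = 640 per group. That allowance concerns immunogenicity and is not used as a drop-out rate below.

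**Inputs.** From the documents: a window of about 10 months, 640 infants per group, and no report scored as no event. Assumed: true 10-month SAE risk R (5% for illustration, 2% to 10% for range), constant hazard, and drop-out proportion D (5% to 20%) independent of SAE risk.

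**Formulas.** Let λ = −ln(1 − R)/10 and μ = −ln(1 − D)/10 per month. SAEs before loss are counted; nothing after loss is.
- Loss spread over the window: crude = λ/(λ + μ) × [1 − exp(−10(λ + μ))]
- All loss at Month 2: crude = (1 − D)R + D[1 − (1 − R)^0.2]

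**Example, R = 5%, D = 10%.** 10λ = 0.0513 and 10μ = 0.1054.
- Spread: (0.0513/0.1567) × (1 − 0.95 × 0.90) = 0.3274 × 0.145 = 4.75%.
- Month 2: 0.90 × 5% + 0.10 × 1.02% = 4.60%.

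**Results for R = 5%**

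| D | Spread: crude (relative shortfall) | Missed per 640 | Month 2: crude (relative shortfall) | Missed per 640 |
|---|---|---|---|---|
| 5% | 4.88% (2.5%) | 0.8 | 4.80% (4.0%) | 1.3 |
| 10% | 4.75% (5.0%) | 1.6 | 4.60% (8.0%) | 2.5 |
| 20% | 4.49% (10.3%) | 3.3 | 4.20% (15.9%) | 5.1 |

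The relative shortfall hardly depends on R. At D = 20% it is 10.3% for R = 2% and 10.2% for R = 10% with spread loss, and 16.0% and 15.8% with loss at Month 2.

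**Missing only the Month 10 call.** With last contact at Month 5, crude = (1 − D)R + D[1 − (1 − R)^0.5]. For R = 5% this is 4.75% at D = 10% and 4.51% at D = 20%, relative shortfalls of about 5% and 10%.

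**Side-by-side of groups.** The standard error of the difference at R = 5% is √(2 × 0.05 × 0.95 / 640) = 1.22 points.
- Equal drop-out: with true risks of 6% and 4%, the risk ratio stays at 1.50 at 10% or 20% drop-out in both groups. The difference shrinks from 2.0 to 1.90 or 1.80 points.
- Drop-out 10% against 20%, true 5% in both: 4.75% against 4.49%, a spurious 0.26 points (0.40 if lost at Month 2), about 0.2 to 0.3 SE.
- Drop-out 10% against 25%: 4.75% against 4.35%, 0.40 points. If lost at Month 2, 4.60% against 0.75 × 5% + 0.25 × 1.02% = 4.01%, about 0.60 points. These are about 0.3 and 0.5 SE.

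**The case against.** The strongest reply is that safety here is descriptive and the loss is already disclosed. Analyses outside the co-primary criteria are descriptive (Protocol 10.9), and no SAE difference, ratio or test between groups is planned. Withdrawals are tabulated by group and reason (Protocol 10.6), sites try to contact infants who miss visits, and an independent committee reviews safety by group. SAEs recorded before loss count. The named intussusception risk falls mostly within 7 days of Dose 1 (Protocol 6.6), so later loss hides mainly background events and constant hazard is a rough assumption. Protocol 10.8 does not itself prescribe an SAE percentage; that comes from the general rule and Template 23.

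All of this stands, and it limits the point. But tabulating withdrawals shows the loss without correcting the percentage.

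Three stronger readings are tempting and not supported:
- A reader might take the sample-size allowance, "Assuming that approximately 35% of enrolled subjects might withdraw or not be evaluable for analyses of immunogenicity", as expected drop-out. That would give shortfalls of about 19% (spread) and 28% (Month 2). But the allowance also covers infants excluded for out-of-window visits, missing serology or forbidden products, who stay in SAE follow-up. It forecasts no SAE follow-up loss.
- A reader might cite the deviation "Short follow-up: subjects who completed the last study contact before the minimum length of follow-up requirement (180 days" in SAP 5.3 as evidence of early loss. It covers infants who did complete the last contact, only too soon, and it is reported by group.
- A reader might conclude that the comparison of groups is unreliable. That needs unequal drop-out. Site staff know the allocation, so imbalance is possible, but the documents give no evidence of it and parents are blinded.

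**Conclusion.** The point holds in a limited form. As written, the rule makes the per-group SAE percentage to Month 10 too low whenever there is any loss to follow-up, and no planned analysis corrects for it. The likely size is modest: a relative shortfall of 2.5% to 10% for 5% to 20% evenly spread drop-out, or 4% to 16% if all loss is at Month 2. Any distortion between groups is well under one standard error for a drop-out imbalance of 10 to 15 points.

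These figures rest on constant hazard, drop-out independent of SAE risk, and drop-out rates that are assumed because the documents give none. If infants with SAEs are more likely to be lost, the understatement is larger. This is a worthwhile correction to a descriptive estimate; it does not affect the co-primary conclusions.

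**What to change.** 1. In Protocol 10.5 and SAP 11.2.5, state that for SAEs the rule equating no report with no event does not extend past an infant's last contact.
2. In Protocol 10.8 and SAP 6.4.1, keep the crude number and percentage. Add one supportive table by group giving follow-up time and either infants with an SAE per 100 infant-months to last contact, or Kaplan-Meier cumulative incidence to Month 10 censored at last contact.
3. Align the titles of Templates 23 and 24 with the Month 10 window.

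The cost is a few sentences and one table. Protocol 9.2.1 already has withdrawal information documented in the eCRF and refers to a date of withdrawal or last contact, so no new data collection should be needed. The limitation is that both estimates assume drop-out is independent of SAE risk, which the table footnote should say.
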